## 6.2 Secondary Outcomes

Secondary endpoints will be the ability to visualize the common hepatic duct (from the junction to the bifurcation), common bile duct (from the junction to the retroduodenal part) and the cystic duct (from the junction to the infundibulum of the gallbladder).

Other secondary outcomes will be short-term outcomes, procedural characteristics (operating time, intraoperative complications, need for conversion), rate and type of BDI, postoperative care characteristics (type of postoperative admission, length of postoperative stay, intensive care unit stay).

Intraoperative, unpredicted events will be recorded and classified according to a grade of unfavourable intraprocedural events. (**Appendix D**)

Short-term will be defined as within 30 days after surgery or until discharge, if the patient remained in hospital at that time. The size of the excised lesions and patients characteristics were assessed and compared as well.

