## 1. Study summary

Study Title	Safety of laparoscopic ChOlecystectomy performed by Trainee surgeons with different CHolangiographic techniques (SCOTCH)
Internal ref. no. (or short title)	SCOTCH study
Study Design	Multicenter prospective interventional trial
Study Participants	Patients
Endpoints	Primary endpoints Time to reach CVS with the utilisation of three different intraoperative imaging modality during LC performed by ST
Summary of eligibility criteria	
Inclusion Criteria
 
 
- Patient scheduled for elective laparoscopic cholecystectomy
 
- Patient age <math>\geq</math> 18 years
 
- Patient able to give consent to the procedure
 
 
Exclusion Criteria
 
 
- Open cholecystectomy
 
- Emergency laparoscopic cholecystectomy
 
- Allergy towards iodine, lohexol or indocyanine green
 
- Liver or renal insufficiency
 
- Thyrotoxicosis
 
- Pregnancy or lactation
 
- Legally incompetent for any reason
 
- Withdrawal of inclusion consent at any time
 
- Age outside inclusion range
 

Arms of the study	
Group CVS-WL (control group): the CVS is achieved in white light, without the utilization of an intraoperative imaging technique. CVS in white light was selected as the control group since it constitutes the actual recognized standard in clinical practice.
 
Group IOC: the CVS is achieved with the help of intraoperative cholangiography
 
Group NIR-C: the CVS is achieved with the help of near-infrared fluorescence cholangiography

Version and date of protocol amendments	Vers. n.1.1- 15/11/2020
Clinicaltrials.gov Registration number	NCT04863482

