The CVS, more than a technology the others, is a technique, introduced by Strasberg and Brunt in 1995, [23] and it is considered the gold standard to perform a safe cholecystectomy with identification of biliary structures (eg, cystic duct, common hepatic duct, and common bile duct) during dissection. Three criteria are required to achieve the CVS: (1) the hepatocystic triangle must be cleared of adipose and fibrotic tissues; the common bile duct and common hepatic duct must not be exposed; (2) the lower third of the gallbladder must be separated from the liver bed to expose the cystic plate; and (3) 2 and only 2 structures should be seen entering the gallbladder. In this case, the main drawback for ST is the necessity to dissect around the Calot's triangle to demonstrate the CVS. It can become challenging for an attending surgeon to supervise the resident to dissect and demonstrate CVS without any visual landmarks.

The most recently introduced intraoperative imaging technique is the near-infrared fluorescent cholangiography (NIRF-C), described by Ishizawa et al in 2009. [24] The NIRF-C allows a real-time enhanced visualization of the extrahepatic biliary tree by fluorescence. NIRF-C is based on the administration of a fluorophore, the indocyanine green, which is excreted in the biliary system, and on the use of a nearinfrared light source, exciting the fluorophore and enabling the visualization. NIRF-C offers some clear advantages when compared with the conventional cholangiography (real-time visualization of biliary tree, reduced costs, easy learning curve, lack of X-ray exposure, safer dissection of Calot's triangle, and possibility to associate fluorescent angiography to highlight vessels). [34, 35] Additionally, NIRF-C has shown a good potential as a teaching tool for trainees. [1, 36]

Previous report demonstrated the feasibility and safety of NIRFC [37]. Prospective study comparing IOC and NIRFC, that the latter is associated with a shorter duration of operation [38] and confirmed its non-inferiority to IOC to X-ray cholangiography in visualizing the critical junction during LC. [39]

Unfortunately, however, as confirmed the EURO-FIGS registry on fluorescence-guided surgery, there is a wide disparity in terms of protocols for NIRFC, across several European surgical centers, particularly in terms of ICG dose and timing of administration. [40]

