### **5.2 Study groups**

The enrolled patients will be divided into three groups, 1 control group and 2 treatment groups, according to the selected technique to achieve the CVS during LC:

**Group CVS-WL (control group):** the CVS is achieved in white light, without the utilization of an intraoperative imaging technique. CVS in white light was selected as the control group since it constitutes the actual recognized standard in clinical practice.

**Group IOC:** the CVS is achieved with the help of intraoperative cholangiography

**Group NIR-C:** the CVS is achieved with the help of near-infrared fluorescence cholangiography

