## 6.3 Evaluated parameters

- i) Age
- ii) Sex
- iii) ASA scores
- iv) Preoperative work up
- v) Type of procedure (CVS-WL, NIFC, IOC)
- vi) Operative parameters (operative time, intraoperative complications)
- vii) BDI (according to the ATOM, Stasberg's and LAU classification [44-46] **Appendix E**)
- viii) How the BDI was diagnosed intraoperatively
- ix) Duration of cholangiography
- x) Time needed to obtain a CVS
- xi) Post-operative outcomes (post-operative complications, late complications, need of readmission, length of hospital stay)
- xii) Surgeons' ease at performing the procedure (questionnaire on identification of anatomical structures, NASA task load test)
- xiii) Surgeons' satisfaction (visual analog scale)

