## **7.2 Inclusion criteria**

- Patient scheduled for elective laparoscopic cholecystectomy
- Patient age  $\geq$  18 years
- Patient able to give consent to the procedure

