## **8. Study procedures**

### **Critical view of Safety(CVS)**

The CVS has 3 requirements. First, the triangle of Calot must be cleared of fat and fibrous tissue. It does not require that the common bile duct be exposed. The second requirement is that the lowest part of the gallbladder be separated from the cystic plate, the flat fibrous surface to which the non peritonealized side of the gallbladder is attached. The cystic plate, which is sometimes referred to as the liver bed of the gallbladder, is part of the plate/sheath system of the liver. The third requirement is that 2 structures, and only 2, should be seen entering the gallbladder. Once these 3 criteria have been fulfilled, CVS has been attained). The rationale of CVS is based on a 2-step method for ductal identification that was and continues to be used in open cholecystectomy. First, by dissection in the triangle of Calot, the cystic duct and artery are putatively identified and looped with ligatures. Next, the gallbladder is completely dissected off the cystic plate, demonstrating that the 2 structures are the only structures still attached to the gallbladder. Time consumption and includes the period from the initial dissection and the obtaining of an acceptable view according to the previously described criteria in order to safely transect the cystic duct.

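### Groups formed by selected technique are compared on time to CVS with unadjusted tests, but sections 6.2 and 6.3 name no measure of case difficulty; the lesion-size item in 6.2 is a separate, minor carry-over.

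*Protocol*

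**What the plan says.** The last sentence of section 6.2 reads "The size of the excised lesions and patients characteristics were assessed and compared as well". Section 6.3 has no lesion item. Its baseline entries are age, sex, ASA score and "Preoperative work up", the last without further definition. Its operative entries are operative time, complications, duration of cholangiography and time to CVS.

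The study summary gives the primary endpoint as "Time to reach CVS with the utilisation of three different intraoperative imaging modality during LC performed by ST". Section 8 lists what CVS requires, starting with "First, the triangle of Calot must be cleared of fat and fibrous tissue". The background has the same requirement: "the hepatocystic triangle must be cleared of adipose and fibrotic tissues". For CVS, section 8 times "the period from the initial dissection and the obtaining of an acceptable view".

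Section 5.2 divides patients "according to the selected technique to achieve the CVS during LC". Section 5.1 calls the study observational and the summary calls it interventional; neither describes an allocation method. Eligibility is broad: "Patient scheduled for elective laparoscopic cholecystectomy", with emergency surgery excluded in 7.3. For group comparisons, section 9 names a t-test or Wilcoxon test and a chi-squared or Fisher test, with no covariates.

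**The concern.** The timed task is the dissection of tissue that may be scarred. By the protocol's own definition of CVS, fibrosis in the triangle lengthens the primary endpoint whatever imaging is used. Excluding emergency surgery removes operations in the acute phase. It does not exclude an elective patient whose gallbladder is chronically inflamed or scarred.

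In a randomised trial, such cases would be balanced on average. Here the groups follow the selected technique, so they may be unevenly spread, and an unadjusted test would credit the difference to the technique. CVS success, operating time and conversion are exposed in the same way.

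Adjustment can be left to a statistical analysis plan, but data collection cannot. A covariate that nobody recorded is not available to a later model, and an operative finding can be only partly reconstructed from operation notes.

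**Working it through.** **1. Is a difficulty measure named anywhere?**

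- Section 6.2: lesion size (not applicable) and patient characteristics (unspecified).
- Section 6.3: preoperative work-up is undefined. It could hold indication, history or imaging, but not an operative finding.
- Section 9.1: possible effect modifiers are age, sex, BMI and a list that breaks off at liver. Gallbladder inflammation is not among them.
- Appendices A to C (image questionnaire, task load, satisfaction): completed after the operation and open to influence from the technique, so not baseline measures.
- Appendix D: grades intraoperative adverse events, which are outcomes.

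No indication, previous cholecystitis, or inflammation, adhesion or difficulty grade is named.

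**2. How much could this matter?** The protocol gives no figure to reproduce, so this is an illustration. From the protocol: a two-sided 5% test (section 9), and 60 and 300 per group, the two figures in section 9.1 that concern biliary imaging. Assumed, not in the protocol: no true technique effect; easy cases average 25 min; difficult cases take d = 10 or 20 min longer; SD 12 min within each type; 20% difficult in group A and 30%, 35% or 40% in group B; the same clock in both groups.

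- Spurious difference: b = d × (pB − pA)
- Variance in a group: V = 12² + d² × p(1 − p)
- Standard error: SE = √((VA + VB)/n)
- Rejection rate: Φ(b/SE − 1.96) + Φ(−b/SE − 1.96)

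Example with d = 10, 20% versus 40%, n = 60: b = 2 min; VA = 144 + 100 × 0.16 = 160; VB = 144 + 100 × 0.24 = 168; SE = √(328/60) = 2.338; b/SE = 0.855; rejection rate 13.7%.

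Example with d = 20: b = 4 min; VA = 208; VB = 240; SE = √(448/60) = 2.733; b/SE = 1.464; rejection rate 31.0%.

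| Difficult cases, A vs B | n = 60, +10 min | n = 60, +20 min | n = 300, +10 min | n = 300, +20 min |
|---|---|---|---|---|
| 20% vs 20% | 5.0% | 5.0% | 5.0% | 5.0% |
| 20% vs 30% | 7.1% | 11.5% | 16.1% | 38.2% |
| 20% vs 35% | 9.9% | 19.7% | 30.1% | 69.5% |
| 20% vs 40% | 13.7% | 31.0% | 48.1% | 90.5% |

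Simulation (3,000 trials per setting) agrees: 7–11%, 10–21% and 15–31% at 60 per group; 15–38%, 30–68% and 47–90% at 300.

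**3. Sensitivity.** If difficulty adds 0.5 to 1.0 within-type SD (6 to 12 min at SD 12) and the shares are 20% versus 30% to 50%, the range is 5.8% to 32% at 60 per group and 9.2% to 92% at 300.

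**4. Would a baseline test reveal the imbalance?** At 60 per group, a chi-squared test finds 20% versus 30% in about 24% of trials and 20% versus 35% in about 46%. Adjustment should therefore not depend on a baseline p-value.

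**The case against.** **The lesion sentence has nothing to do with the bias.** This is correct. A reader might infer that the wrong variable displaced the right one and so distorts the comparison. It does not: it is left-over text, like the survival analysis in section 9, and deleting it changes no result.

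**Section 6.3 is not a complete data list.** This stands too. Conversion and intensive care stay are outcomes in 6.2 with no entry of their own in 6.3, BMI appears only in 9.1, and the web-based form is not shown. A reader might infer that difficulty goes unrecorded; the document supports only that it is not named. That still matters, because nothing obliges centres to collect it in a uniform way.

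**The selection mechanism is not described.** Section 5.2 does not say who selects, when, or whether by patient or by centre. In the NIR-C group the dye is given at least 45 minutes before imaging, so that choice would normally precede any view of the gallbladder. Imbalance would then come mainly from preoperative knowledge or centre case mix. This makes indication and history at least as important as an operative grade. It does not remove the risk.

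**The clock may differ between groups.** For IOC, section 8 counts time from application of the grasper, after the cystic duct has been dissected. If that is the endpoint clock, most of the dissection delay falls outside it, and the figures above do not transfer to comparisons with IOC.

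**Adjustment works too well in the simulation.** Adding the difficulty indicator returns the error rate to 4–6%, but only because it is the sole confounder and is measured without error. Real data will not behave so well.

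**Conclusion.** The point holds as a conditional one. Non-randomised groups, unadjusted tests and no named difficulty measure leave the comparison of time to CVS, CVS success, operating time and conversion open to confounding that could be only partly corrected afterwards.

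A reader might go further and conclude that these outcomes are biased and beyond repair. The document does not support that. Bias arises only if difficulty differs between groups, and some information may be captured under preoperative work-up or in operation notes.

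The size is illustrative: about 7% to 31% false positives at 60 per group and 15% to 90% at 300, against a nominal 5%. Every input except the sample sizes and the test level is assumed. The range does not estimate this study's error rate. It shows that a spurious difference of 1 to 4 minutes is enough to matter, and more so in a larger study.

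The lesion-size item is a plain error of minor weight.

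**What to change.** 1. In 6.2, delete the size of excised lesions.
2. In 6.3, define preoperative work-up, and add indication for surgery and previous acute cholecystitis (yes/no).
3. In 6.3, add a simple grade of gallbladder inflammation and adhesions. The independent surgeon whom section 6.1 already places in theatre records it at first view, before dissection and before any imaging.
4. In section 9, pre-specify that the between-technique comparisons of time to CVS, CVS success and operating time are adjusted for these items whatever their baseline p-values.

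The cost is two or three form fields, a few seconds of grading per case and one or more model terms, with no extra patients, staff or procedures. There are two limits. The observer may know the technique, and a first-view grade may miss scarring inside the triangle. Grading later would capture more of that scarring but could be influenced by the technique. Adjustment will therefore reduce confounding, not remove it, and the report should say so. If patients have already been operated on, indication and history can probably be taken from their notes, but a standardised first-view grade cannot.

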## 6.3 Evaluated parameters

- i) Age
- ii) Sex
- iii) ASA scores
- iv) Preoperative work up
- v) Type of procedure (CVS-WL, NIFC, IOC)
- vi) Operative parameters (operative time, intraoperative complications)
- vii) BDI (according to the ATOM, Stasberg's and LAU classification [44-46] **Appendix E**)
- viii) How the BDI was diagnosed intraoperatively
- ix) Duration of cholangiography
- x) Time needed to obtain a CVS
- xi) Post-operative outcomes (post-operative complications, late complications, need of readmission, length of hospital stay)
- xii) Surgeons' ease at performing the procedure (questionnaire on identification of anatomical structures, NASA task load test)
- xiii) Surgeons' satisfaction (visual analog scale)

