With laparoscopic surgery, there is also loss of haptic input and stereoscopic depth perception, which predisposes to the misperception that leads to BDI [20] Various methods have been described to help the identification of the structures in Calot's triangle; these include intraoperative cholangiogram (IOC) [22], critical view of safety (CVS) [23] and the near-infrared fluorescent cholangiography (NIRF-C) [24].

Each of these technique have been proved to be useful and, at the same time, to have some intrinsic drawback that could be amplified when in unexperted hands.

The use of IOC during LC is well established [25] with the aim to detect of bile duct stones, defining biliary tree anatomy and the early recognition of iatrogenic common bile duct (CBD) injuries. [26-29]

Although regarded as a safe procedure with a low risk of complications, the merits of routine IOC usage remain an area of debate. Some studies suggest that it adds significant operating time and cost, without reducing the risk of detection of retained CBD stones or bile duct injury. [30-33] Others

demonstrated that the routine use of IOC for cholecystectomy plays a crucial role in the detection of intraoperative CBD stones and CBD injury.

It could be argued, however, that to perform IOC it is necessary to incise what is presumed to be the CD, which in itself may be the cause of a lateral injury of the CBD (or CHD) in case of mistaken anatomy [30] and, in a training setting, IOC can be difficult to teach and residents do not gain enough experience with it as not all surgeons perform it routinely and that [1]

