## **5. Patients and study design**

### **5.1 Study design**

The study will be a multicentre prospective observational study. Members of the Italian Society of Endoscopic Surgery [SICE] will be invited to participate. All participating centers will be required to register the study according to local regulations. Evidence of successful registration should be sent to your national network committee prior to beginning of data collection.

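### Technique is selected rather than randomised, and suspected bile duct stones are neither excluded nor a named data item, so secondary comparisons with IOC can be confounded by indication

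*Protocol*

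**What the plan says.** Protocol section 5.1 states the design: "The study will be a multicentre prospective observational study". The summary table in section 1 calls the trial interventional, but neither place gives randomisation or any other allocation rule. Section 5.2 forms the three groups "according to the selected technique to achieve the CVS during LC".

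Section 4 describes the purpose of IOC: "The use of IOC during LC is well established [25] with the aim to detect of bile duct stones". It also reports studies in which routine IOC "plays a crucial role in the detection of intraoperative CBD stones and CBD injury". It gives no such purpose for white light or for near-infrared cholangiography.

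The indication criterion for entry in section 7.2 is "Patient scheduled for elective laparoscopic cholecystectomy". Section 7.3 lists nine exclusions, and none concerns bile duct stones.

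The secondary outcomes in section 6.2 include "procedural characteristics (operating time, intraoperative complications, need for conversion", together with length of postoperative stay. Section 6.3 lists 13 headings to be recorded. They include an undefined pre-operative work-up item (iv), "Operative parameters (operative time, intraoperative complications" (vi), duration of cholangiography (ix), time to the critical view (x), and post-operative outcomes including late complications and readmission (xi). Section 9 compares continuous variables by t-test or Wilcoxon test and discrete variables by chi-squared or Fisher's test, with no adjustment.

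**The concern.** When the technique is chosen case by case, the reason for choosing it matters. The protocol itself supplies one reason for choosing IOC that has nothing to do with showing a trainee the anatomy: looking for stones in the duct. If patients in whom stones are suspected go to IOC more often than to the other groups, the IOC group differs at baseline in a feature that can itself affect operating time and stay.

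The study aims to name the best technique for training (section 4) and to propose a standard (section 5.3). Operating time, complications and stay are part of the evidence for that. A difference due to who was sent for cholangiography could be read as a difference due to the imaging. If the pre-operative suspicion is not collected, no later analysis can separate the two.

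**Working it through.** The protocol gives no figure on this point to reproduce, so the check follows the chain through the text and then asks whether a size can be derived.

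1. **Could stones be a reason to choose IOC?** Yes. Section 4 describes IOC as used "with the aim to detect of bile duct stones, defining biliary tree anatomy", and stones come first in that list.

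2. **Can that reason decide the group?** Yes. Group follows the selected technique (section 5.2), no allocation rule is given anywhere, and sections 5.5 and 14 place all procedures within usual care. The word interventional in section 1 does not supply a rule.

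3. **Are such patients in the study?** Yes. Any elective laparoscopic cholecystectomy in a consenting adult qualifies (section 7.2), and none of the nine exclusions removes known or suspected duct stones (section 7.3).

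4. **Will the data identify them?** Not by any named item. Sections 6.2 and 6.3, the IOC procedure in section 8 and the IOC questionnaire in Appendix A contain nothing on stones suspected, found or cleared. Item iv of section 6.3 might be meant to include pre-operative suspicion, but it is not defined. Item ix times the cholangiogram; it neither gives the reason for it nor separates stone-related time.

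5. **Does the analysis allow for it?** No. The tests in section 9 are unadjusted. Section 9.1 mentions an exploratory look at effect modifiers such as age, sex and body mass index. Duct stones are not in the legible part of that list, and effect modification is a different question from confounding.

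6. **How large is it?** Let p(IOC) and p(other) be the shares of patients with known or suspected stones in the IOC group and in a comparison group. Let d be the difference in mean outcome between patients with and without that indication, technique held fixed. If d is the same in both groups, the confounding in the crude difference is

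   bias = [p(IOC) − p(other)] × d.

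   The protocol gives neither share, nor d, nor a standard deviation for any of these outcomes. The bias in minutes or days, and its effect on the false-positive rate, therefore cannot be computed from the document.

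7. **Which way does it go?** For operating time, p(IOC) > p(other) and d > 0 are both plausible, so the likely sign is against IOC. For stay the same argument is possible but weaker. For readmission and late complications the sign is open, because stones missed in the other two groups could raise these events there, and item xi records them in all groups.

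8. **Is the primary endpoint affected?** Largely not. It is the time to reach the critical view (section 1), recorded separately as item x. The point concerns secondary outcomes.

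**The case against.** The case on the other side is substantial, and much of it stands.

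- **A reader might infer that time spent on stones found at IOC is itself a bias against IOC.** The protocol does not support that. If IOC reveals a stone and the operation lengthens, that is a consequence of using IOC, and total operating time properly includes it. Moreover, the IOC procedure in section 8 contains no clearance step: once the ducts are identified, cholangiography ends and the gallbladder is removed. Clearance in the same session would be an inference. Only the choice of technique by prior indication is confounding.
- **A reader might infer a bias of known direction on every outcome, or put a number of minutes on it.** Neither is available. Readmission and late complications could move against the other groups, and any figure in minutes would be the product of an assumed share and an assumed duration.
- **A reader might infer that IOC has a proven benefit which the study ignores.** Section 4 calls routine IOC debated, and also reports studies finding added time and cost without benefit for stones or injury.
- **The work-up item may already cover suspected stones.** Section 6.3 is a list of headings and not a case-report form, so the supportable statement is that the item is undefined, not that it omits the indication. It could not, however, cover stones found or cleared during surgery.
- **The root problem is the missing allocation rule, and stones are one confounder among several.** True. This one still deserves its own line because the protocol itself names it as an aim of one technique, and correcting for it needs a specific baseline field.
- **A statistical analysis plan, which is not shown, could deal with it.** It could add an adjustment or an analysis set, but it cannot use a variable that was never collected. Eligibility and the recorded parameters are fixed in this protocol.

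**Conclusion.** The point holds as confounding by indication in the secondary comparisons. Followed as written, the protocol lets patients with a clinical reason for cholangiography gather in the IOC group, does not name that reason as a data item, and compares the groups without adjustment. The conclusion rests on two assumptions: that suspected stones influence the choice of technique at some centres, and that such patients differ in operating time or stay for reasons other than the technique. Both are plausible, but the protocol does not quantify either.

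The size is therefore unknown. The likely direction is against IOC for operating time, possibly so for stay, and undetermined for readmission and late complications. The primary time to the critical view is largely unaffected. The change should be made because it is cheap and because a baseline indication not captured at the time may not be recoverable. It is not a flaw that invalidates the primary comparison.

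**What to change.** **Section 6.3.** For every patient in every group, record whether bile duct stones were known or suspected before surgery, whether stones were found during surgery, and any time spent on duct clearance. The first field could be added by defining the pre-operative work-up item so that it includes it.

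**Section 9.** Pre-specify the comparison of secondary outcomes in patients without a pre-operative indication for cholangiography, or adjusted for that indication, and report it alongside the result in the full set.

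**Reporting.** Keep total operating time as the outcome. Time net of duct clearance may be given as a supplementary description only, since it conditions on a finding made after the technique was applied. Report stones found descriptively. Do not compare them between groups as an outcome, because the protocol describes only IOC as looking for duct stones and the comparison would reflect detection ability.

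**Cost.** A few extra case-report fields, one added sentence in section 9, and a somewhat smaller set for that analysis. No change to treatment or to the handling of stones is implied.
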